New knowledge is needed to reduce this healthcare disparity and care gap for African-American patients who would otherwise benefit from clozapine treatment. To generate this knowledge, the objectives of the study are:

Aim 1: To study and understand the normal pattern of white blood cell fluctuations in BEN patients. We will study 250, mostly African ancestry, patients to determine the fluctuations of within-participant WBC and ANC (mean, S.D., frequency and duration of episodes of mild, moderate or severe neutropenia), measured weekly over a period of (up to) 6 weeks

Hypothesis:

BEN patients will have lower mean ANC and WBC than normal values reported in the literature. The normal variation in ANC and WBC will create sporadic episodes with ANC below guidelines in BEN patients.

Aim 2: To test to see if people with BEN have a genetic risk that may put them at risk of having a naturally lower WBC count than people who are White. We will establish ANC and WBC patterns in both those with and without the *DARC* allele.

We will also genotype a panel of variants in the human leukocyte antigen (*HLA*) complex gene recently shown to be associated with agranulocytosis in Caucasian patients, to explore the prevalence of co-occurrence of these *HLA* variants and the *DARC* null genotype in BEN patients, which might increase risk of agranulocytosis in AA and SSA participants with BEN. We anticipate that the high risk *HLA* variants will be in very low frequency in the AA and SSA population

*Hypothesis: Patients with the *DARC* null allele genotype will have lower ANC and WBC than people without the *DARC* null allele genotype.*

Aim 3: To test the safety of clozapine treatment in people with BEN. We also will study the normal fluctuations of WBCs and ANCs during 6 months of clozapine treatment. We will study the risk of potential episodes of agranulocytosis or serious infection. We will develop an upper 95% confidence interval for risk of agranulocytosis ($< 500 \text{ cells/mm}^3$), which may be compared to the known 1% agranulocytosis risk in European ancestry populations treated with clozapine. We will also estimate the risk of serious infection in clozapine-treated BEN patients.

Hypothesis 1 (DARC null allele patients):

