Side Effect Checklist (SEC): This scale is designed to assess vital signs and directly inquire about 25 commonly occurring antipsychotic side effects. Specifically, it covers side effects seen with clozapine, side effects that relate to infection (i.e., sore throat, gum soreness, cold, pneumonia) and other common side effects. We will provide anticonstipation medications and other side effect medications as needed.

GENOTYPING INFORMATION:

- Single-Nucleotide Polymorphism (SNP) genotyping will be performed on gDNA isolated from blood or saliva with QIAamp DNA Maxi Kit (Qiagen) using TaqMan polymerase chain reaction (PCR) technology.
- We will use a validated commercially available 5'->3' exonuclease assay; Assay IDs; (C__15769614_10) and (C__2493442_10) for determining the genotype at the Duffy variant (rs2814778) and missense mutation (rs12075) of *DARC* gene.
- We will use the context sequence of genomic regions for the SNPs extracted from the GWAS study of clozapine-induced agranulocytosis to design forward and reverse primers and design customized assays for genotyping the SNPs that met genome wide significance for association with clozapine-induced agranulocytosis in the CIAG study. Customized genotyping assays will be used to genotype SNPs, rs41549217 and rs13073300, for *HLA-B* and *HHLA2* genes, respectively, and SNPs rs143211074 and rs28362679 of *BTNL2* gene. All PCR will be performed in [name] Lab, on standard 96-well reaction plates, as previously described. For each PCR reaction, 2 ng of genomic DNA will be used in a 5- μ l reaction mixture (1.3 mM MgCl₂, 200 μ M dNTP mix, 0.25 μ M of each primer, 5% DMSO, 1.5 U Taq polymerase). The PCR program includes: denaturation of DNA (5 min at 94°C), 30 cycles of 30s at 94°C, 30s at 62°C, and 30s at 72°C. This will be followed by a final extension of 10 min at 72°C.
- All PCR reactions will be performed using the Biorad Multiplatform Thermocycler, which has 4 blocks of 384 wells (Bio-Rad Laboratories Inc., Hercules, CA, USA). PCR results will be read by reporter dye fluorescence (Vic/Fam) and allelic discrimination analysis with 7900 Sequence Detection Systems (SDS) software v2.3 (Applied Biosystems) to assign genotype groups to the SNPs. The TaqMan genotyping assay is quick and accurate and has worked well for our research team on this project.

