An exploratory study of fluctuations in WBC and ANC in clozapine-treated African descent participants meeting ANC criteria for BEN who are not *DARC* null homozygotes will use statistical methods similar above. In addition, we will review patient characteristics and medical history to determine any identifiable causes of episodes of benign neutropenia in this group, to further describe this subgroup of potentially heterogeneous origins. While

underpowered to obtain definitive results, this substudy will provide valuable initial data to characterize this subgroup and the potential risks and benefits of clozapine.

An exploratory study of HLA alleles associated with agranulocytosis will provide descriptive data on the percentages (plus or minus 95% CI) of these *HLA* alleles (*HLA-B* and *HHLA2*) in participants with BEN by *DARC* null genotype to provide valuable preliminary data on to whether routine screening for these *HLA* risk alleles could enhance safety of clozapine treatment in AA patients with BEN.

RISKS AND DISCOMFORTS:

- i. Risks related to study medication (Therapeutic Risk). This study involves the treatment with clozapine.

Other than neutropenia (see below), the main risks to clozapine treatment are as follows: salivary hypersecretion, somnolence, weight increase, dizziness, constipation, nausea, vomiting, dyspepsia, tachycardia, hypotension, type II diabetes, hyperlipidemia, sweating, and dry mouth. Serious but rare side effects include: seizures, myocarditis, sudden death, tardive dyskinesia, neuroleptic malignant syndrome, pulmonary embolism, hepatitis, fever, intestinal blockage, respiratory and cardiac arrest. We will be closely monitoring weekly for side effects at all sites and will have standardized operating procedures across sites for close monitoring standards. Standard routine medical care will be given for all side effect occurrences. The only treatments not permitted are those that may lead to a risk of neutropenia. No benzodiazepines should be administered in the first 3 days of dose titration of clozapine.

- ii. Risk of neutropenia or infection (Side Effect Risk)

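### Rare risk-allele percentages are planned with a plus-or-minus interval, which fails at counts near zero, and the two genotyped BTNL2 SNPs appear in no analysis

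*Combined protocol and SAP*

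**What the plan says.** The last paragraph of Statistical Analyses describes an exploratory study that "will provide descriptive data on the percentages (plus or minus 95% CI) of these" HLA alleles, naming HLA-B and HHLA2 in brackets, split by DARC null genotype. The stated use is preliminary evidence on whether routine screening for risk alleles could make clozapine safer. The paragraph gives no interval method, expected frequency or denominator, and does not say whether the percentage counts people or chromosomes.

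Aim 2 gives the expectation: "We anticipate that the high risk *HLA* variants will be in very low frequency in the AA and SSA population".

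Genotyping Information sets out the panel. It was chosen as "the SNPs that met genome wide significance for association with clozapine-induced agranulocytosis in the CIAG study". It consists of one SNP each for two genes ("Customized genotyping assays will be used to genotype SNPs, rs41549217 and rs13073300, for *HLA-B* and *HHLA2* genes, respectively") and, in the same sentence, "SNPs rs143211074 and rs28362679 of *BTNL2* gene".

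For agranulocytosis, the other outcome expected to be rare, the plan is more careful. Risk of Agranulocytosis - Analysis and Power warns that large-sample intervals may perform poorly with few cases and turns to a binomial limit. Safety Monitoring then uses Clopper-Pearson limits in Table 1.

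**The concern.** A percentage with a plus-or-minus margin normally means the estimate and an equal distance either side, that is, the normal approximation. That approximation is poor when the expected count is close to zero, which is what Aim 2 predicts. If no carrier is found, the result would be 0% with a margin of 0%, which reads as if the alleles had been shown to be absent. For a question about screening, the informative number in that case is the upper limit.

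The second part concerns completeness. The BTNL2 SNPs entered the panel for the same reason as the other two, yet no analysis mentions them. A reader of the results could not tell whether they were examined, and the answer on screening would cover only part of the panel.

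**Working it through.** **The plan's own figures.** The allele analysis states no figure to reproduce. As a check on the plan's rare-event method:
- The zero-case one-sided limit for agranulocytosis is 1 − 0.05^(1/212) = 1.40%, matching the stated 1.4%.
- Clopper-Pearson limits at n=212 agree with Table 1 to within 0.0001, except the upper limit for 2 cases, printed as 0.0037 and computed as 0.0337. That is a separate matter.

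**Inputs.**
- n = 212: the number of DARC-null homozygotes anticipated in Statistical Analyses (given there as 212 or more). Safety Monitoring also reaches 212 as 250 less 15% dropout (250 × 0.85 = 212.5).
- 424 chromosomes = 2 × 212, if alleles are counted instead of carriers.
- n = 38 for participants who are not null homozygotes. This is an assumption (250 − 212); the plan does not state the size of that group.
- Carrier rates of 0.25%, 0.5% and 1%. These are assumptions; the plan says only that the frequency is very low.

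**Formulas.** With k carriers among n and p = k/n:
- Symmetric (Wald): p ± 1.96 × √(p(1 − p)/n). At k = 0 the margin is 0. The lower limit is negative when k < 3.84 × (1 − k/n), which at these sample sizes means k = 1, 2 or 3.
- Exact (Clopper-Pearson): at k = 0 the two-sided 95% upper limit is 1 − 0.025^(1/n). For k > 0 the limits come from beta quantiles.

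**Limits at n = 212.**

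| Carriers | Symmetric 95% | Exact 95% |
|---|---|---|
| 0 | 0 to 0% | 0 to 1.72% |
| 1 | −0.45 to 1.39% | 0.01 to 2.60% |
| 2 | −0.36 to 2.24% | 0.11 to 3.37% |
| 3 | −0.17 to 3.01% | 0.29 to 4.08% |
| 4 | 0.06 to 3.72% | 0.52 to 4.76% |

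Exact upper limits at a count of 0 for other denominators:
- 250 people: 1.46%
- 424 chromosomes: 1 − 0.025^(1/424) = 0.87%
- 38 people (assumed): 1 − 0.025^(1/38) = 9.25%

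Wilson limits are close to the exact ones (0 of 212: 0 to 1.78%).

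**How often this would happen at n = 212.** Coverage is the sum of the binomial probabilities of every count whose interval contains the true rate.

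| Assumed carrier rate | P(0 carriers) | P(3 or fewer) | Symmetric coverage | Exact coverage |
|---|---|---|---|---|
| 0.25% | 59% | 99.8% | 41% | 98.3% |
| 0.5% | 35% | 98% | 65% | 97.7% |
| 1% | 12% | 84% | 88% | 97.9% |

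Most of the lost coverage is the zero-count case: at 0.25%, 59% of trials would give a zero-width interval that misses the true rate. In an assumed stratum of 38, symmetric coverage at the same three rates would be 9%, 17% and 32%.

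**The SNP lists side by side.**
- Genotyping Information: rs41549217 (HLA-B), rs13073300 (HHLA2), rs143211074 and rs28362679 (both BTNL2).
- Exploratory HLA analysis: HLA-B and HHLA2 only.

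BTNL2 appears nowhere in the document outside Genotyping Information.

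**The case against.** The strongest reply is that the plan names no Wald interval or normal approximation. The phrase may be loose shorthand for a percentage with its 95% confidence interval, written by authors who, in the same section, recognise that large-sample limits can fail. This stands in part. A reader might infer that the plan commits to an invalid method, or that a zero-width interval will be published. The text supports neither. It supports a wording that is symmetric if taken literally, a method left unspecified, and an exact-limit safeguard written for agranulocytosis only.

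The numerical inputs are also open to challenge, and these points stand:
- The carrier rates are not in the documents.
- The figure of 38 is not a stated stratum size, because 212 is also the sample left after dropout.
- Genotyping blood is drawn at the screening visit, so dropout from treatment need not reduce the genotyped sample, and 212 may not be the denominator.
- The paragraph speaks of alleles, so chromosomes may be meant, which halves the exact upper limit at a count of zero.

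None of this changes the pattern of zero width at 0 and a negative lower limit at 1 to 3, which holds at every denominator tried.

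On BTNL2, one could infer that half the panel will go unreported. That goes too far: the bracketed list may be incomplete, or a deliberate restriction in a paragraph about HLA alleles. What can be said is that no analysis mentions these two SNPs and no reason is given.

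Finally, the analysis is exploratory and descriptive, with no test, threshold or effect on participants. If counts and denominators are published, a reader can compute exact limits. This limits the importance of the point but does not argue against the change.

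**Conclusion.** The point holds as a minor improvement. Taken as written, the interval would be uninformative at a count of 0 and would have an impossible lower limit at 1 to 3, and these are likely counts for very rare variants. At 0 of 212 the difference is 0 to 0% against 0 to 1.7% for carriers; on 424 chromosomes the exact upper limit is 0.9%. If the non-homozygous group were about 38, its exact upper limit at 0 carriers would be about 9%. The coverage figures of 41% to 88% rest on the assumed carrier rates, the literal symmetric reading and n=212. The BTNL2 mismatch depends on none of these assumptions. Neither part bears on the primary outcomes or the sample size.

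**What to change.** In the exploratory HLA paragraph of Statistical Analyses:

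1. Replace the plus-or-minus wording with exact (Clopper-Pearson) 95% confidence limits, the method already used for Table 1. Wilson limits would also do.
2. State whether the percentage is of carriers or of alleles, and report counts with denominators.
3. Report all four SNPs listed in Genotyping Information, including both BTNL2 SNPs, by DARC genotype. If the BTNL2 SNPs are left out on purpose, say so and give the reason.

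The cost is a sentence or two of text, slightly wider intervals and two more table rows. No new sampling is needed, because the genotyping blood draw is already scheduled at Visit 1 and the assays are already specified.

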- Once a participant is discontinued from clozapine, for whatever reason, they may remain in the study for continued monitoring. When any participant is discontinued from the study, completion ratings and assessments (including laboratory tests and rating scales) will be performed if possible. If a patient is prematurely terminated from the study, the investigators will work with the clinical team to ensure the patient will continue clozapine or resume other antipsychotic treatments for their symptoms. More information on discontinuation is later in the protocol in the withdrawal criteria section.

Brief Psychiatric Rating Scale (BPRS): Total symptoms will be measured using the total score on the 18 item version. Psychotic symptoms will be calculated using the conceptual disorganization, hallucinations, suspiciousness and unusual thought (delusion) items.

Clinical Global Impression Scale (CGI): The CGI severity of illness item will be used to assess global changes in symptomatology.

Calgary Depression Rating Scale (CDS): This 9-item scale is designed specifically to assess depressive symptoms in patients with schizophrenia. The CDS has been shown to be reliable and have good construct validity. The CDS total score will be used to measure depressive symptoms and assess suicidal ideation and actions. Suicidality may be decreased with clozapine, however we will monitor the suicide item for changes during the study.

Retrospective chart review will be conducted to compliment and confirms the data collected by in person interviews already completed

SIDE EFFECT MONITORING

All side effect scales will be performed monthly with exception of Side Effect Checklist, which will be done at each visit.

Simpson-Angus Extrapyrarnidal Symptom Rating Scale (SAS): The modified 11-item version of the SAS will be used to assess EPS.

Abnormal Involuntary Movement Scale (AIMS): This is a 12-item scale, with 7 items designed to assess abnormal facial, oral, extremity, and trunk movements; 3 global judgment items; and 2 current dental status items.

Barnes Akathisia Scale (BAS): This is a 4-item scale designed to assess objective and subjective components of akathisia.

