also include dosage adjustment or increase. If serious suicidal ideation or intent is observed during clozapine treatment, the “suicide prevention plan” will be implemented immediately and if patients do not respond to a dose increase or other treatments, they will be discontinued from study. The “suicide prevention plan” consists of immediate psychiatric evaluation, implementation of a suicide prevention plan, provision of 24 hour access to a physician, referral to emergency services as necessary and continued evaluation using the CDS.

Protection from research interview and data-gathering-related risks.

In previous studies with the target population, we have developed procedures for conducting interviews in a manner that is sensitive to the needs of the participants and the emotional nature of the interviews, while maintaining high scientific standards. Several of the strategies that we have successfully used to minimize the potential distress for participants include: informing participants before the interviews about the topics that will be covered in the interview; reminding participants that they may choose not to answer certain questions, or to terminate the interview at any time; and taking breaks during the interview when the participant feels tense or distressed. Interviewers will be trained in the recognition of, and appropriate response to (including the involvement of other professionals), specific kinds of participant negative responses.

Certification on Protection of Human Subjects in Research:

All research staff participating in this study at all three sites are required to undergo the online Collaborative Institutional Training Initiative (CITI) Course on Human Subjects Research. Their certificates of completion are uploaded (as research staff) in the University of Maryland Baltimore IRB-approved study protocol in CICERO (Collaborative Institutional Comprehensive Evaluation of Research Online) – the University of Maryland School of Medicine's Research Evaluation Portal and are compliant with the Health Insurance Portability and Accountability Act (HIPAA).

Federal Certificate of Confidentiality:

We will be obtaining a Federal Certificate of Confidentiality in the US. This is not required for Nigeria.

Collaborative Protocol and Consent Form Approval:

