We have criteria for discontinuation of clozapine and the ability to continue regular monitoring. Participants can stop study drug and continue in the monitoring portion of the study.

- A. Clozapine Discontinuation Criteria (clinician and PI opinion, following are potential causes of discontinuation).

Symptom Worsening:

Either the treating psychiatrist, medically accountable physician, or the PI may determine that a patient is experiencing clinical worsening. Clinical worsening may be defined as the following: the subject is judged to be entering an exacerbation of his/her illness by the treating clinician; an increase of 3 or more points from baseline on a BPRS positive symptom item; an increase of 3 or more points from baseline on BPRS somatic concern, conceptual disorganization or hostility; or an increase of 2 or more points from baseline on the CGI global severity rating or in the case the CGI is at a ceiling for beginning, clinical judgment will be made. Transient rating changes do occur so the symptom increases must be accompanied by the clinician's feelings that they are entering exacerbation.

No symptom Improvement

Clozapine discontinuation may take place in the case of no adequate symptom response to clozapine and discontinuation is thought to be a better option. Response is defined as 20% improvement and a final score of ≤ 35 in total BPRS score or CGI ≤ 3 . These scores generally result in a response rate of approximately 68% with another 25% demonstrating partial response. We anticipate that 7% of patients may not achieve any response (partial or full) and may be discontinued.

Low White Blood Cell Count

If a participant drops below 500 cells/mm³ (with stat redraw for confirmation) than clozapine will be discontinued. Participants may be discontinued due to a rapid falling white blood cell count if the hematologist or PI has reason to be concerned at a higher level.

Significant Side Effects.

The clinical and research team may discontinue clozapine if the participant is having significant side effects or side effects that are not in the best interest of the patient to continue for safety reasons. This will be determined by the research study team along with clinical team.

Medication Nonadherence

Clozapine discontinuation for more than two consecutive days will need re-titration. If this happens more than once as nonadherence the participant may be discontinued from clozapine

Non-adherent to Study Procedures

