If the participant is nonadherent to white blood cell monitoring, clozapine will be discontinued.

Once a participant is discontinued from clozapine, for whatever reason, they may remain in the study for continued monitoring.

B. Discontinuation from Study and all Monitoring:

- All attempts, as long as participant agrees, to follow-up monitoring when clozapine is stopped will occur
- Discontinuation from the study will occur if the participant is not adherent to study procedures and blood draws or if the participant no longer wants to be enrolled or the physician determines blood draws and/or study participation are not in the best interest of the patient
- If a patient is discontinued from open label clozapine for reasons described above, they will continue as usual for the follow-up lab work, symptom ratings and clozapine blood levels
- If the patient is recommended for clozapine discontinuation or study termination the PI or medically accountable physician will meet with the participant to describe why they are recommended for clozapine discontinuation or study termination.
- If the participant is discontinuing clozapine the research and clinical team will work together to ensure a plan for followed medication treatment in order to help with the appropriate titration of a new medication. This will be done clinically with no research protocol for cross titration and other medication treatment.
- If the participant is discontinuing clozapine but continuing in the study for monitoring no additional expectations are required
- When any participant is terminated from the study altogether, the study team will schedule with the participant as soon as possible to complete ratings and assessments (including laboratory tests and rating scales). This may result in a midweek visit. The participant will be compensated for any study visit time.
- If a participant is discontinued from clozapine they will continue, if they agree, to continue the follow-up monitoring for the entire 6 month treatment period.
- If a participant is nonadherent with blood work during clozapine they will be terminated from the study and no further data collection will occur past the final assessments.

BENEFITS:

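### Read literally, the Suicidality section takes participants with unresponsive serious suicidality out of research follow-up, while those who stop clozapine for any reason may stay to month 6 (minor; cheap to fix)

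*Combined protocol and SAP*

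**What the plan says.** The Suicidality section provides that, when serious ideation or intent is seen on clozapine, a suicide prevention plan starts at once and "if patients do not respond to a dose increase or other treatments, they will be discontinued from study". Besides immediate psychiatric evaluation, that plan includes "provision of 24 hour access to a physician, referral to emergency services as necessary and continued evaluation using the CDS".

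The protocol treats stopping clozapine separately in several places:

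- Withdrawal Criteria, opening: "Participants can stop study drug and continue in the monitoring portion of the study".
- Symptom Monitoring: "Once a participant is discontinued from clozapine, for whatever reason, they may remain in the study for continued monitoring".
- Withdrawal Criteria, part B, on participants taken off clozapine: "they will continue, if they agree, to continue the follow-up monitoring for the entire 6 month treatment period".

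Part B is headed "Discontinuation from Study and all Monitoring". For anyone leaving the study altogether it schedules closing ratings and laboratory tests. Symptom Monitoring and the section on adequate psychiatric response plan these only if possible. One exit has an explicit end to data collection. Participants non-adherent with blood work while on clozapine are told that "they will be terminated from the study and no further data collection will occur past the final assessments".

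The Data and Safety Monitoring Plan sends all SAEs to the DSMB, the principal investigators and the IRB. It gives no collection window after study exit.

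**The concern.** The two routes give an odd ordering. A participant who stops clozapine for an ordinary reason can be observed to month 6. A participant whose serious suicidality has not resolved is, on the wording, taken out of the study. That is a foreseeable high-risk state: the Suicidality section itself notes that suicidality may be raised in treatment-resistant patients.

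At stake is the completeness of general safety data. Primary Outcome Variables names patient safety alongside ANC levels and side effects. A later attempt, death or other serious event in one of these participants could fall outside what the study records and what the DSMB sees. The clinical decision whether clozapine should continue is properly left to the treating team and is not in question.

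**Working it through.** This is mainly a comparison of texts, followed by one check on the agranulocytosis figure.

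**1. What the trigger leads to.** The rule in the Suicidality section is mandatory and names the study, not the drug. Suicidality is named neither in the clozapine-stop list (Withdrawal Criteria, part A) nor among the study-exit reasons (part B), so those lists do not settle which is meant.

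**2. What follows each route.**

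| Route | Follow-up described |
|---|---|
| Clozapine stopped, any reason (Symptom Monitoring; Withdrawal Criteria) | Monitoring to the end of the 6-month period, if the participant agrees. Laboratory Monitoring separately plans 4 more weeks of weekly counts. |
| ANC <500 (Monitoring Guidelines, item 6) | Likely study exit and no further visits, but the team contacts the clinical team and records the outcome of the event. |
| Unresponsive serious suicidality (Suicidality) | Study exit. Completion ratings and laboratory tests if possible. Suicide prevention plan with continued CDS (Calgary Depression Rating Scale) ratings, duration not stated. |
| Second treatment gap needing re-titration (Medication Adherence) | Study exit, though the participant may go on taking clozapine under local care. |

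**3. Whether another provision closes the gap.**

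- The suicide prevention plan protects the patient clinically but does not mention SAE or vital-status recording after exit.
- The chart review is described thus: "Retrospective chart review will be conducted to compliment and confirms the data collected by in person interviews already completed". It is tied to past interviews, not to later events.
- SAE reporting has recipients but no period after exit.
- The outcome check for ANC <500 is limited to that event.

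None of these sets SAE or vital-status collection after a suicidality exit.

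**4. The agranulocytosis limit.** Inputs: 250 enrolled, 15% dropout and n = 212 (Safety Monitoring), and the zero-case formula 0.05 = (1 − r)^n (Risk of Agranulocytosis).

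- 250 × 0.85 = 212.5, so n = 212 reproduces. Allowed withdrawals: 250 − 212 = 38.
- r = 1 − 0.05^(1/212) = 0.01403, so the stated 1.4% reproduces.
- The 212 is already net of withdrawals for causes other than agranulocytosis. Suicidality exits belong among those 38, so the limit stays at 1.40%.
- Sensitivity, on an assumption the documents do not supply: if 0.5% to 5% of 250 (1 to 12 people after rounding) were lost on top of the 15%, n would be 211 to 200 and the limit 1.41% to 1.49%.

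**The case against.** The strongest reply is that the protocol does not keep its terms apart, so the sentence may only mean stopping the drug. There is good evidence for this:

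- Symptom Monitoring has a phrase that attaches study discontinuation to clozapine itself.
- A second treatment gap leads to study exit under Medication Adherence but to a possible clozapine stop under Withdrawal Criteria, part A.
- ANC <500 leads to likely study exit in Monitoring Guidelines but to a clozapine stop in part A.

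Symptom Monitoring also refers the reader to Withdrawal Criteria for more on discontinuation. There, unresponsive suicidality could count as an exacerbation under part A, with monitoring kept open. Part B promises efforts at follow-up whenever clozapine stops and the participant agrees. It also allows exit when participation is not in the patient's best interest, and sparing someone in crisis from research procedures is defensible.

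Much of this stands. Follow-up may well be intended, and the best-interest clause should remain. But the Suicidality sentence still says study exit without conditions, and three sites could apply it differently. Nor does the reply supply any SAE or vital-status collection where exit does occur.

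A reader might infer that the protocol forbids all data after a suicidality exit. It does not say so: the explicit end to data collection belongs to non-adherence with blood work, and the end to visits in Monitoring Guidelines belongs to ANC <500. A reader might also infer that these patients are left without care. The suicide prevention plan, and the commitment to work with the clinical team on further treatment, contradict that.

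**Conclusion.** The point holds as a minor inconsistency with a safety consequence. On its literal wording, the Suicidality section removes from research follow-up participants who, had they simply stopped clozapine, would be offered monitoring to month 6. No SAE or vital-status collection is set after that exit, so later serious events could go unrecorded. This rests on reading the sentence as written; if the sponsor means a clozapine stop only, the remedy is to say so.

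No size is claimed. The documents give no rate of serious suicidality, of non-response or of exit timing, so any count of participants or weeks lost would be assumption throughout. That the group is small is itself an assumption.

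A reader might infer that the agranulocytosis result is biased. The documents do not support that. The planned 1.4% limit already allows for other withdrawals, and the binomial calculation uses all clozapine-treated participants whatever their follow-up. Only an actual missed case would move it (1 case in 212 gives a one-sided limit of 2.22%), and nothing in the documents links suicidality exits with agranulocytosis.

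**What to change.** Reword the Suicidality sentence so that the treating clinicians decide whether clozapine continues or stops. The participant, if they agree, then stays in the safety follow-up already offered in Withdrawal Criteria, part B, to the end of the 6-month period. That follow-up should cover SAEs, vital status, ANC and CDS.

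Keep the best-interest clause in part B. Where full exit is needed, make one status check with the clinical team at month 6, with the participant's consent, and record SAEs and vital status. Monitoring Guidelines already does something similar for the outcome of ANC <500 events.

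The same single check may be applied, with consent, to the Medication Adherence exit, where participants can leave the study while still taking clozapine.

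The cost is a wording change and a small amount of extra follow-up for what are likely to be a few participants, using procedures largely in place.
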